**Document date: 10.01.2020**

**NCT: NCT03837028.**

## **The effect of being diagnosed with human papillomavirus infection on women's sexual lives**

### **Materials and Methods**

The present prospective observational study was conducted with women referred to our gynecology outpatient clinic upon being diagnosed with an HPV infection by the community based cervical cancer screening program. After obtaining the ethical approval (approval number: 2017/33) from our hospital's local ethics committee, the patients who had been diagnosed with a high-risk HPV (HPV 16, 18, 31, 33, 35, 39, 45, 51, 52, 56, 58, 59, 68, 69, and 82) infection for the first time in their lives and who were sexually active and in the reproductive period were included in this study. All the patients were  $\geq 30$  years old (cervical cancer screening with co-test starts at the age of 30 years in Turkey).

Post-menopausal women, and patients with the low-risk HPV genotypes (HPV 6 or 11), sexual penetration disorders, chronic systemic diseases, a sexual abuse history, or a prior HPV infection, and those under any antidepressant medication or diagnosed with psychiatric disorders were excluded from the study. Additionally, patients who did not agree to participate in the study after reading the informed consent form and those who did not come for the follow-up visit were also excluded.

The patients who met the inclusion criteria were informed about the details of the study and were asked whether they would have liked to participate in this study. Written informed consent was obtained from all the patients who agreed to do so. The sociodemographic data of these patients, such as pregnancy, parity, Body Mass Index (BMI), educational level, and marital status were recorded. We had the participants filled out the FSFI and BAI questionnaires at the first visit to assess the initial sexual functions and anxiety levels of the women. Then the participants were informed about their co-test results and were divided into four groups according to their HPV genotypes and cytology results as follows: Group 1, HPV 16/18-positive and normal cytology; Group 2, HPV 16/18-positive and abnormal cytology; Group 3, non-16/18 HPV-positive and abnormal cytology; and Group 4, non-16/18 HPV-positive and normal cytology.

The detailed information, including the sexually transmitted nature, occurrence rate, and progress of the disease, as well as the relationship between high- vs. low-risk HPV types and the development of CIN or cervical cancer were explained to the participants by a clinical

expert. After all the participants had undergone a routine gynecologic examination, they were informed about the treatment and follow-up plans. The management of the patients with abnormal co-test results was planned according to the American Society for Colposcopy and Cervical Pathology (ASCCP) guidelines. All of the patients were called in two months later for a follow-up to assess the changes in their anxiety levels and sexual functions by using the FSFI and BAI questionnaires. The patients in groups 1, 2, and 3 were directly referred to colposcopy per ASCCP guidelines, and the patients in group 4 were referred to colposcopy upon their gynecologist's suspicion of a cervical lesion. All of the patients were informed about the colposcopy procedure at their first visits, and colposcopy was performed on the patients at their second visits.

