### **Statistical Analysis**

Data analysis was performed by using SPSS (IBM SPSS Statistics for Windows, Version 20.0. Armonk, NY: IBM Corp.). A one-sample Kolmogorov–Smirnov test was performed to analyze the distribution of the clinical variables. The frequencies and percentages of the categorical variables and the mean, standard deviation, median, and range values of the continuous and ordinal variables are presented. The study groups were compared using Oneway analysis of variance (ANOVA) and the Kruskal Wallis H tests for the parametric and non-parametric

variables, respectively. The Bonferroni correction was performed for posthoc analyses of the significant differences in the second-visit BAI score among the study groups. The Wilcoxon rank test was used for the comparison of the BAI and FSFI scores at the first and second visits. For all the calculations, a p-value of  $< .05$  was considered statistically significant.

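### The four groups cross genotype with cytology, but no overall genotype or cytology difference is estimated; adding two-factor contrasts beside the four-group test would be a cheap improvement

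*Combined protocol and SAP*

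**What the plan says.** Under Materials and Methods, women are "divided into four groups according to their HPV genotypes and cytology results". The first three groups are "Group 1, HPV 16/18-positive and normal cytology; Group 2, HPV 16/18-positive and abnormal cytology; Group 3, non-16/18 HPV-positive and abnormal cytology", and the last is "Group 4, non-16/18 HPV-positive and normal cytology". Two yes/no results (HPV 16/18; abnormal cytology) thus give four cells, and all four are present.

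Under Statistical Analysis, "The study groups were compared using Oneway analysis of variance (ANOVA) and the Kruskal Wallis H tests", the choice between the two depending on distribution. The only follow-up step described is this: "The Bonferroni correction was performed for posthoc analyses of the significant differences in the second-visit BAI score among the study groups". The other inferential analysis is within women: "The Wilcoxon rank test was used for the comparison of the BAI and FSFI scores at the first and second visits". It is given no genotype or cytology term.

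Management also differs between the groups. Materials and Methods states: "The patients in groups 1, 2, and 3 were directly referred to colposcopy per ASCCP guidelines". Group 4 was referred only if the gynaecologist suspected a lesion.

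The document gives no sample size, group sizes, expected difference or standard deviation. It specifies no genotype term, cytology term, interaction, averaged contrast, or effect estimate with a confidence interval.

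**The concern.** A one-way test treats the groups as four unrelated labels. If it is significant, it says that some group differs, not whether the difference goes with the genotype or with the smear. The follow-up pairs answer this only in part. Two of them change both results at once, so a difference there cannot be assigned to either, and the absence of a difference can hide two that cancel. If all pairs are tested, these two also take a share of the Bonferroni allowance. For FSFI no follow-up step is described, so a significant four-group result on sexual function would have no planned route to an explanation.

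At stake is whether the study can say which part of the result goes with higher anxiety or poorer sexual function, by how much, and with what uncertainty.

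**Working it through.** The plan has no figure to reproduce. The structural check uses only the document; the numerical check rests on assumed group sizes and differences.

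**1. What each pair changes.** Group definitions and the referral rule are from Materials and Methods. Statistical Analysis lists no pairs, so taking all six is an inference.

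| Pair | Genotype | Cytology | Referral rule |
|---|---|---|---|
| 1v2 | same | differs | same |
| 2v3 | differs | same | same |
| 1v4 | differs | same | differs |
| 3v4 | same | differs | differs |
| 1v3 | differs | differs | same |
| 2v4 | differs | differs | differs |

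Four pairs change one test result and two change both. Only 1v2 and 2v3 change one test result under the same referral rule.

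**2. Why the mixed pairs mislead.** Suppose HPV 16/18 and abnormal cytology each add 0.5 SD. The means for groups 1 to 4 are then 0.5, 1.0, 0.5 and 0 SD. Pair 1v3 gives 0.5 − 0.5 = 0, and pair 2v4 gives 1.0 − 0 = 1.0 SD. Neither is the effect of one factor.

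**3. Precision.** Assume n per group and a common SD. One pair has variance 2·SD²/n. The cytology contrast, (mean of 2 and 3) − (mean of 1 and 4), has variance ¼·4·SD²/n = SD²/n, and the genotype contrast has the same. The ratio of standard errors is 1/√2 = 0.71. At n = 50 this is 0.141 v 0.200 SD.

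With unequal groups the gain varies. For 30/20/50/100 (assumed), the contrast variance is ¼(1/30 + 1/20 + 1/50 + 1/100) = 0.0283 SD². The pairs have 0.0833 (1v2), 0.0700 (2v3), 0.0433 (1v4) and 0.0300 (3v4), so the contrast barely improves on 3v4.

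**4. Power.** Assume a 0.4 SD cytology difference, no genotype difference, no interaction, equal groups and two-sided tests. The four-group test has 3 df, alpha 0.05 and noncentrality n·4·0.2² = 0.16n (noncentral F). The factor contrast is at 0.05/2 and the single pair at 0.05/6 (normal approximation).

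| n per group | Four-group test | Factor contrast | One pair |
|---|---|---|---|
| 30 | 41% | 48% | 14% |
| 50 | 64% | 72% | 26% |
| 80 | 86% | 91% | 46% |

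Against the four-group test, the contrast gains 7, 8 and 5 points. If the contrast were instead tested at 0.05/6, its power would be 33%, 58% and 83%, below the four-group test.

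**5. If the pattern follows referral.** Suppose groups 1 to 3 sit 0.4 SD above group 4. Each averaged contrast is then (0.4 + 0.4)/2 − (0.4 + 0)/2 = 0.2 SD. At n = 50 the four-group test has 51% power and each averaged contrast about 20%. Replacing the four-group test would lose power here.

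**The case against.** The strongest defence is that the plan already does much of what is asked. A reader might infer from the one-way test that genotype and cytology are never examined separately. The document does not support that: four of the six pairs change one test result only, so for second-visit BAI such differences can be tested within a level of the other factor. What is missing is an overall contrast and an estimate with its interval.

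A reader might also infer that the planned test is invalid or inflates error. It does neither. Nor does the document support the inference that the study fails its own objective: the title concerns the effect of being diagnosed, follow-up is for changes in anxiety and sexual function, and separating the two results is not a stated aim.

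The gap between one pair and a factor contrast (26% v 72% at n = 50) invites the reading that power is badly lost. That is the wrong comparator for a conclusion that the type of result does not matter, because such a conclusion would follow from a non-significant four-group test. On that comparison the gap is 5 to 8 points.

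Finally, the referral rule sets three groups against one, which in a 2x2 is an interaction pattern, so assuming no interaction is doubtful here. An interaction test would be a weak guide: for a 0.4 SD interaction (difference of differences, two-sided 0.05) its power is about 19%, 29% and 43% at n = 30, 50 and 80.

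All of this stands, and it narrows the point. It does not supply the missing estimates. For FSFI, where no pairwise step is described, it leaves the gap untouched.

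**Conclusion.** The point holds as a low-cost improvement to a valid analysis. The 2x2 structure, the absence of any overall genotype or cytology estimate for BAI or FSFI, and the two mixed pairs follow from the document alone, except that the set of six pairs is inferred. The benefit is mainly interpretability, together with factor estimates whose standard error is 0.71 times that of one pair when groups are equal. The power gain over the four-group test is modest. It depends on equal groups of 30 to 80, a 0.4 SD difference in one factor, no interaction and testing two contrasts at 0.05/2, none of which the document gives. Under a three-versus-one pattern the four-group test is the stronger, so it should stay. No analysis of these groups fully separates the test results from the referral rule.

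**What to change.** In Statistical Analysis, keep the four-group test and add the following for second-visit BAI and second-visit FSFI:

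- Fit a prespecified model with genotype (16/18 or not), cytology (abnormal or normal) and their interaction, with the first-visit score of the same instrument as covariate. Use robust standard errors if the scores are non-normal.
- Report the genotype contrast (1+2 v 3+4, averaged equally over cytology) and the cytology contrast (2+3 v 1+4, averaged equally over genotype) with confidence intervals.
- Always show beside them the four single-factor contrasts 1v2, 3v4, 1v4 and 2v3. Do not choose between the two sets on an interaction test.
- Do not attribute 1v3 or 2v4 to either factor.
- Name the contrasts that will be tested and apply the multiplicity correction to those.
- State that group 4 alone was not directly referred to colposcopy. Pairs 1v4 and 3v4 and both averaged contrasts therefore also carry the referral difference, and only 1v2 and 2v3 compare groups under the same referral rule.

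The methods are written in the past tense. If outcomes by group have already been seen, the added model should be labelled as post hoc.

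The cost is some added wording and slightly more analysis of data already collected, with no new patients or measurements. The downsides are averaged contrasts that are less informative if the factors interact, and more comparisons to account for.

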### **Cervical Cancer Screening and the Management Strategy**

According to the Turkish national cervical cancer screening program, the initial cervical screening test is recommended at the age of 21 years, and women < 30 years old are screened with the Papanicolaou (PAP) test alone every three years. Women  $\geq$  30 years old are screened with co-testing (HPV testing alongside liquid-based cervical cytology) every five years. If HPV test results are positive, then HPV genotyping is performed, and the PAP test is cytologically evaluated. If HPV test results are negative, then the PAP test is not evaluated. Patients with HPV 16/18 (regardless of the cytology status) or those infected with HPV strains other than 16/18 (non-16/18 HPV-positive) and exhibit abnormal cervical cytology are referred to a specialist for colposcopy. For non-16/18 HPV-positive patients who exhibit normal cervical cytology, an additional co-test is recommended 1 year after the index test. However, if the gynecologist has a clinical suspicion of a cervical lesion, these patients may also be referred for colposcopy.

### **HPV Diagnosis and Genotyping:**

In Turkey, HPV testing for cervical cancer screening is performed at primary level healthcare centers, such as KETEM (Kanser Erken Teşhis, Tarama ve Eğitim Merkezi; Cancer Early Diagnosis, Screening and Educational Centers). Two cervical swab samples are taken from the patients. The first sample is collected and smeared onto a glass slide for cytological analysis. The second sample is collected with a different brush, and the tip of the brush is broken and then placed into a 5-ml Standard Transport Medium (STM) for HPV DNA analysis. Samples across the country are delivered into two national laboratories for the cervical cancer screening program. In these laboratories, the Hybrid Capture 2 (Qiagen, Germany) system is used for HPV DNA analysis. This system detects 13 different high-risk HPV genotypes (HPV16, 18,

31, 33, 35, 39, 45, 51, 52, 56, 58, 59, and 68) and reports the results as positive or negative. HPV-DNA–positive samples are genotyped with the CLART® kit (Genomica, Madrid, Spain). The results about HPV status, HPV genotype, and cytology (when HPV-positive) are recorded into a National Screening software system and sent to the patient's family physician/nurse at primary healthcare centers.

### **Beck Anxiety Inventory**

The BAI questionnaire consists of 21 questions and is a brief assessment of anxiety with an emphasis on somatic symptoms. It was developed to measure anxiety and depression levels, and the inventory has been validated for the Turkish population. Participants indicate how much they have been bothered by each symptom over the past week. Responses are rated on a 4-point Likert scale, and range from 0 (not at all) to 3 (severely). Total score is calculated by summing the rates from the 21 questions. It is classified as follows: a score of 0–21 = low anxiety, a score of 22–35 = moderate anxiety, a score of  $\geq 36$  = potentially concerning levels of anxiety.

### **Female Sexual Function Index**

Sexual dysfunction was assessed via a self-administered FSFI questionnaire which had been adapted to the Turkish population by Aygin et al. This is a 19-item questionnaire that contains the following six domains: desire, arousal, lubrication, orgasm, satisfaction, and pain. The scores are ranked from 0–5 for the arousal, lubrication, orgasm, and pain domains; and 1–5 for the satisfaction and desire domains. Domain scores were obtained by summing the rates from the questions in each domain and then multiplying them with the following domain factors: 0.6 for desire, 0.3 for arousal and lubrication, and 0.4 for orgasm, satisfaction, and pain. The total score was obtained by summing the six domain scores. The FSFI scores ranged from 2.0 to 36.0, with higher scores indicating better sexual function and categorized into four groups: normal sexual function (total FSFI score  $\geq 26.55$ ), mild risk for a female sexual disorder (FSD) (total FSFI score 18–26.55), moderate risk for FSD (total FSFI score 11–17), and severe risk for FSD (total FSFI score  $\leq 10$ ).

### **Statistical Analysis**

Data analysis was performed by using SPSS (IBM SPSS Statistics for Windows, Version 20.0. Armonk, NY: IBM Corp.). A one-sample Kolmogorov–Smirnov test was performed to analyze the distribution of the clinical variables. The frequencies and percentages of the categorical variables and the mean, standard deviation, median, and range values of the continuous and ordinal variables are presented. The study groups were compared using Oneway analysis of variance (ANOVA) and the Kruskal Wallis H tests for the parametric and non-parametric

variables, respectively. The Bonferroni correction was performed for posthoc analyses of the significant differences in the second-visit BAI score among the study groups. The Wilcoxon rank test was used for the comparison of the BAI and FSFI scores at the first and second visits. For all the calculations, a p-value of  $< .05$  was considered statistically significant.

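### The four non-randomised groups are compared with no stated adjustment for first-visit BAI or FSFI and no stated between-group test of change

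*Combined protocol and SAP*

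**What the plan says.** Materials and Methods describes a prospective observational study. On the first visit it says: "We had the participants filled out the FSFI and BAI questionnaires at the first visit to assess the initial sexual functions and anxiety levels". It continues: "Then the participants were informed about their co-test results and were divided into four groups according to their HPV genotypes and cytology results". All women were recalled two months later "to assess the changes in their anxiety levels and sexual functions by using the FSFI and BAI questionnaires". Both scores therefore exist at both visits for every woman analysed.

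The Statistical Analysis section gives two separate analyses.

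- Between groups: "The study groups were compared using Oneway analysis of variance (ANOVA) and the Kruskal Wallis H tests for the parametric and non-parametric" variables. The sentence names neither the variables nor the visit. The post hoc sentence names one outcome: "The Bonferroni correction was performed for posthoc analyses of the significant differences in the second-visit BAI score among the study groups".
- Between visits: "The Wilcoxon rank test was used for the comparison of the BAI and FSFI scores at the first and second visits". It does not say whether this was done overall or within each group.

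The section mentions no covariate, regression model, group-by-visit term or between-group comparison of change.

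**The concern.** Nothing in the design balances first-visit anxiety or sexual function across groups defined by genotype and cytology. If the groups already differed when the first questionnaires were completed, a comparison of second-visit scores carries some or all of that difference forward, and it can be read as an effect of the test result. The reverse can also happen: a group that starts lower and truly rises can end level with the others, and the raw test sees nothing. Even with balanced groups, ignoring a correlated first-visit score costs precision.

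The Wilcoxon test does not close the gap. It asks whether scores moved between visits, not whether they moved by different amounts in different groups. Any conclusion that genotype or cytology category affected anxiety or sexual function rests on the between-group comparison.

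**Working it through.** The documents state no sample size, power, SD, group sizes or visit correlation, so there is no figure of the plan's own to reproduce.

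**Inputs from the documents.** Four groups (Materials and Methods); significance level .05 (Statistical Analysis).

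**Assumed inputs.** 50 women per group; normal scores with SD 1 at each visit; visit correlation rho = 0.3/0.5/0.7; one group differing by b SD at the first visit. Two cases bracket what happens to b by the second visit: it regresses to rho × b, or it is stable at b.

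**What each method leaves when the result has no effect**

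- Raw second-visit score: shift rho × b (regressing) or b (stable), SD 1.
- ANCOVA: shift 0 (regressing) or b(1 − rho) (stable), residual SD √(1 − rho²). For b = 0.5, stable: shift 0.35/0.25/0.15 on SD 0.95/0.87/0.71.
- Change score: shift −b(1 − rho) (regressing) or 0 (stable), SD √(2 − 2rho).

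**Rejection rates.** Raw and change-score rates come from the noncentral F distribution with 3 and 196 degrees of freedom and noncentrality n × (shift/SD)² × 3/4. For the stable 0.5 SD raw case this is 50 × 0.25 × 0.75 = 9.375, which gives 72%. For the regressing raw case it is 0.84/2.34/4.59, which gives 10/22/40%. ANCOVA and conditional rates come from 20,000 simulated studies per setting.

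| 0.5 SD first-visit difference, no effect of the result | Regressing | Stable |
|---|---|---|
| Raw second-visit ANOVA | 10/22/40% | 72% |
| ANCOVA | 5% | 42/27/16% |
| Change scores | 29/22/14% | 5% |

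Kruskal-Wallis on the raw score behaves much like ANOVA: 10/20/38% and 69–70%.

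**Range for the raw test**

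- Smaller differences, 50 per group: 7/10/16% (regressing) or 30% (stable) at 0.3 SD; 6/7/10% or 15% at 0.2 SD.
- 0.5 SD with 25 per group: 8/13/21% or 40%.
- 0.5 SD with 100 per group: 17/41/72% or 96%.

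**If first-visit scores were compared and found non-significant.** A first-visit ANOVA misses a 0.5 SD difference in 28% of studies. Among those, the raw second-visit test rejects in about 6/8/10% (regressing) or 61/52/39% (stable). The reassurance is fair in the first case and poor in the second.

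**Power with a balanced first visit and a true 0.5 SD effect in one group.** Raw 72%; ANCOVA 76/85/96%; change scores 56/72/92%.

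**Masking.** If one group starts 0.5 SD lower (stable) and truly rises 0.5 SD, its second-visit mean equals the others, so the raw test rejects at 5%. ANCOVA rejects in 10/27/67% and change scores in 56/72/92%.

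**Within-group Wilcoxon tests read side by side.** With an identical true change of 0.4 SD in all four groups, some but not all groups reach significance in about 79–87% of simulated studies (25 per group) or 24–84% (50 per group). Such a pattern is not evidence that change differs.

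**The case against.** Several points on the other side have force.

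- **Change is analysed.** A reader might infer that the stated aim of assessing change goes unmet. The documents do not support that: the Wilcoxon test compares the visits, and no objective says that change should differ between groups. The gap is confined to between-group conclusions.
- **The compared variables are not named.** First-visit or change scores may have been among them, so it cannot be said that they were not compared. The text does not say that they were, and a first-visit comparison would neither adjust nor test change.
- **No imbalance is shown.** The exclusions for psychiatric disorders, antidepressants, chronic disease, sexual abuse and penetration disorders remove some sources of it. With no true first-visit difference the raw test holds 5% and only precision is lost. This stands, and it limits the point to a risk.
- **The remedy is not always better.** Change scores do worse than the raw test for a regressing difference at correlation 0.3 (29% against 10%). Two co-equal analyses would also give two chances: at least one rejects in about 7–8% of fully null studies, and in 16–31% (regressing) or 18–43% (stable) with a 0.5 SD difference. This also stands, and it is why one analysis should be primary.
- **The first visit may not precede all knowledge of the result.** The study took "women referred to our gynecology outpatient clinic upon being diagnosed with an HPV infection by the community based cervical cancer screening program", and results on HPV status, "HPV genotype, and cytology (when HPV-positive) are recorded into a National Screening software system and sent to the patient's family physician/nurse". A reader might infer that women already knew their genotype or cytology. The documents do not say so; they place the explanation of the co-test results after the questionnaires. Knowledge of HPV positivity alone, acting equally in all groups, would cancel between groups. Knowledge of genotype or cytology would not.
- **Adjustment does not reach everything.** Groups 1–3 were referred directly to colposcopy and group 4 only on suspicion, with the procedure at the second visit. Baseline adjustment cannot remove a difference of that kind.

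**Conclusion.** The point holds as an omission in the stated analysis. The groups are not randomised, both scores are available at the first visit, and no stated between-group analysis uses them. Under the assumed inputs, ANCOVA rejects less often than the raw test in every null case with a first-visit difference that was examined, and it has more power when the first visit is balanced. It does not cure a stable difference (42/27/16% at 0.5 SD).

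A reader might go further and infer that the between-group findings are biased. The documents give no first-visit scores by group, so they cannot show this. All rates are conditional on the assumed group size, normality, correlation and imbalance. That the omission exists is clear from the text. How much the fix gains is less certain, because it depends on what women knew at the first visit. The unnamed ANOVA/Kruskal-Wallis variables and the unstated scope of the Wilcoxon test are missing detail; the point does not depend on them.

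**What to change.** For BAI and for FSFI total, make one analysis primary for between-group conclusions: ANCOVA of the second-visit score on group, with the first-visit score of the same scale as covariate, in rank-based or robust form if the scores are skewed. Report confidence intervals and apply Bonferroni over the 4 × 3/2 = 6 pairwise contrasts (.05/6 = .0083).

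Report the between-group comparison of change scores as a sensitivity analysis, not as a second route to significance. Keep the raw second-visit comparison as description.

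State that the two analyses can disagree in non-randomised groups, because ANCOVA holds its error rate if a first-visit difference regresses and change scores do so if it is stable. State also that neither makes the groups exchangeable. Say what women knew of their results when they completed the first questionnaires, which scores are compared between groups, and whether the Wilcoxon test is pooled or within group.

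The cost is one extra model per outcome, one sensitivity analysis and a few sentences, on data already collected. The real downside arises if genotype or cytology was already known. If half of a true 0.5 SD effect were present at the first visit, ANCOVA would keep 1 − 0.5 × rho = 85/75/65% of it, with power 57–62% against 72% for the raw test. Change scores would keep 50%, with power 16/22/34%.

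### No adjusted comparison of BAI or FSFI is planned between the non-randomised genotype/cytology groups, although suitable covariates are recorded, so the group contrasts may be confounded

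*Combined protocol and SAP*

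**What the plan says.** All references are to the combined protocol and SAP.

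- **Design.** Materials and Methods opens: "The present prospective observational study was conducted with women referred to our gynecology outpatient clinic". Women "were divided into four groups according to their HPV genotypes and cytology results as follows". Test results therefore decide membership; there is no randomisation, matching or stratification.
- **Covariates.** The same section states that sociodemographic data "such as pregnancy, parity, Body Mass Index (BMI), educational level, and marital status were recorded". The words that open the list show that it is not exhaustive. Age must be known, because entry requires an age of at least 30.
- **Outcome timing.** Participants "filled out the FSFI and BAI questionnaires at the first visit to assess the initial sexual functions and anxiety levels of the women", before the co-test results were explained. The second measurement follows at two months: "All of the patients were called in two months later for a follow-up to assess the changes in their anxiety levels and sexual functions".
- **Between-group analysis.** The Statistical Analysis section says: "The study groups were compared using Oneway analysis of variance (ANOVA) and the Kruskal Wallis H tests". It does not list the variables compared. It adds a Bonferroni step for post-hoc contrasts of second-visit BAI, the only outcome it names for a group contrast. For categorical variables it gives frequencies and percentages and names no test.
- **Within-woman analysis.** A Wilcoxon test compares first- and second-visit BAI and FSFI.

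No regression, ANCOVA or stratified analysis is described.

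**The concern.** One-way ANOVA and Kruskal-Wallis are one-factor tests. In groups that were not randomised, a difference in second-visit BAI or FSFI combines any effect of the co-test result with any difference in who is in each group. Comparing baseline characteristics across groups does not cure this, because a non-significant baseline test does not show that confounding is absent.

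Adjusting for the first-visit score alone might also fall short. After that score was taken, women were given "The detailed information, including the sexually transmitted nature, occurrence rate, and progress of the disease". If marital status, education or age alters how a woman reacts to this news, the influence arises after the first-visit score and is not captured by it.

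At stake is the reading of a group difference as a consequence of genotype or cytology. Bias of this kind does not shrink with more women. A larger sample only makes a biased difference more likely to reach significance.

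**Working it through.** **Nothing to reproduce.** The document states no sample size, group size, SD, effect size or covariate distribution. Only the 0.05 significance level and the number of groups (four) come from it. Every other input below is an assumption.

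**1. Size of bias, one binary covariate.**
Bias = (difference in covariate share between two groups) × (difference in second-visit BAI between covariate levels).
Assume that the share of unmarried women differs by 10 to 30 percentage points and that their second-visit BAI differs by 3 to 6 points:
- low: 0.10 × 3 = 0.3 points
- high: 0.30 × 6 = 1.8 points

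The 3 to 6 points is a difference in second-visit level. Part of it could already exist at the first visit, which is one reason to include the first-visit score in the model.

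**2. False-positive rate of one pairwise contrast with no true group effect.**
SE = 10 × √(2/n), with an assumed SD of 10. This gives 1.826 for n = 60 and 1.414 for n = 100.
Rate = P(Z > z − bias/SE) + P(Z < −z − bias/SE).
Four groups give 4 × 3/2 = 6 pairs. The document does not state how many are tested. If all six are, the Bonferroni level is 0.05/6 = 0.0083 and z = 2.638 (two-sided, also an assumption).

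| n per group | Bias (points) | Bias/SE | Rate at 0.83% (Bonferroni) | Rate at 5% (no correction) |
|---|---|---|---|---|
| 60 | 0.3 | 0.164 | 0.9% | 5.3% |
| 60 | 1.8 | 0.986 | 4.9% | 16.7% |
| 100 | 0.3 | 0.212 | 1.0% | 5.5% |
| 100 | 1.8 | 1.273 | 8.6% | 24.7% |

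The Bonferroni column is the relevant one for post-hoc BAI. It ignores the requirement that the overall test be significant first, which can only lower these rates. At the high end the inflation is 4.9/0.83 ≈ 6-fold and 8.6/0.83 ≈ 10-fold. At the low end it is negligible.

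**3. Overall four-group ANOVA.**
One continuous covariate is shifted in one of four equal groups, with no true group effect. Bias in SD units = imbalance (SD) × correlation with the outcome. Rates come from the noncentral F distribution at nominal 0.05.

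| Imbalance | Correlation | Bias (SD) | n = 25 | n = 50 | n = 100 |
|---|---|---|---|---|---|
| 0 | any | 0 | 0.050 | 0.050 | 0.050 |
| 0.2 SD | 0.1 | 0.02 | 0.050 | 0.051 | 0.052 |
| 0.5 SD | 0.3 | 0.15 | 0.075 | 0.103 | 0.166 |
| 0.5 SD | 0.5 | 0.25 | 0.125 | 0.216 | 0.412 |

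In simulation (4,000 runs per scenario), putting the covariate in the model brought the rate to 0.045–0.052 in all six scenarios run, which took imbalances of 0 or 0.5 SD and correlations of 0.3 or 0.5.

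**The case against.** **Confounding is not shown.** It needs a covariate related to both group and outcome. The document gives no covariate data by group and no reason why marital status or education should differ between genotypes or cytology results. A reader might infer that the group differences are confounded as a matter of fact. The document supports only that they may be, and the bias is nil if the groups are balanced.

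**The covariates may be compared across groups.** A reader might also infer that they enter no group comparison at all. The sentence on ANOVA and Kruskal-Wallis does not name its variables, so BMI and parity may be compared as baseline characteristics. What is missing is an adjusted comparison of BAI or FSFI.

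**Eligibility already restricts.** Entry is limited to sexually active women of reproductive age, at least 30 years old, with a first high-risk diagnosis. Psychiatric disorders, antidepressants, chronic systemic disease, sexual abuse history and penetration disorders are excluded. This narrows the age range and removes several likely confounders, and that part of the objection stands. It does nothing for marital status or education.

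**Bonferroni is planned.** The 16.7% and 24.7% figures are therefore not error rates of the planned post-hoc BAI contrasts. This stands, and the Bonferroni column should be used. The correction deals with multiplicity, however, and leaves the bias in place.

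**The before-after comparison is sound on this point.** In the Wilcoxon test each woman is her own control for fixed traits. This stands in full, but that test makes no contrast between groups.

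**Conclusion.** The point holds as a limitation of the between-group contrasts. Groups defined by test result are compared with unadjusted one-factor tests although the covariates for an adjusted analysis are recorded. The second-visit BAI contrast is the clearest case; any FSFI contrast between groups is open to the same bias.

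The size is unknown. On the assumed inputs the false-positive rate for one Bonferroni-corrected BAI contrast runs from about nominal (0.9% against 0.83%) to 8.6%. The overall ANOVA runs from 5% to about 41%. These ranges rest wholly on assumed imbalance, covariate effect, SD and group size, and are not estimates for this study. The document gives no means of telling which end applies, and that is why a low-cost adjusted analysis is worth adding.

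A reader might extend the criticism to the study's main question, the effect of being diagnosed. The document does not support that extension on these grounds, because fixed differences between women do not affect the first-versus-second-visit comparison.

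**What to change.** For second-visit BAI and for second-visit FSFI, fit one linear model on group, first-visit score, age, marital status, education, parity and BMI. Use robust standard errors, or a rank-based version if the scores are skewed. Fix the covariate list before fitting.

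Report adjusted group differences with 95% CIs beside the unadjusted tests, with a table of baseline characteristics by group. Base the between-group conclusion on the adjusted result. If the model is not fitted, label the group contrasts as unadjusted and descriptive.

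State one remaining limit. Materials and Methods says "The patients in groups 1, 2, and 3 were directly referred to colposcopy per ASCCP guidelines", while group 4 was referred only on clinical suspicion. Covariate adjustment cannot separate the test result from this difference in referral, so a contrast of group 4 with the others reflects both.

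The cost is one extra model per outcome on data already recorded, a few degrees of freedom, and possibly merging sparse categories of marital status or education.
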